Statistical Methodology	
Aim 1: Principal Component Analysis for metabolomics data; two-way ANOVA [regimen (HIIT vs. MICT vs. CON) \times time (base vs. immediate post vs. 1h post)]
 
Aim 2: Two-way mixed-factorial ANOVA for counterregulatory hormones; Comparison of area under the curve across all trials for CGM, aggregated over 24 hrs
 
Aim 3: Spearman correlations between metabolomic outcome and physiological variables)

Abbreviations and Definition of Terms

Abbreviations and Definitions of Terms	
Abbreviation:	Formal Title:
HIIT	High Intensity Interval Training
MICT	Moderate Intensity Continuous Training
T1D	Type 1 Diabetes
CON	Control (no exercise)
CGM	Continuous Glucose Monitoring
HbA1c	Hemoglobin A1c
VO ₂ peak	Peak Oxygen Consumption
PAR-Q+	Physical Activity Readiness Questionnaire
BMI	Body Mass Index
4C Model	Four Compartment Model
FM	Fat Mass
%fat	Percent Body Fat
LM	Lean Mass
DXA	Dual-energy x-ray Absorptiometry Total Body Scan
BIS	Bioelectrical Impedance Spectroscopy
VT	Ventilatory Threshold
HR	Heart Rate
HR _{max}	Maximal Heart Rate
TIR	Time-in-Range
CHO	Carbohydrate
PRO	Protein
FAT	Fat
NDSR	Nutrient Data System for Research
ELISA	Enzyme-Linked Immunosorbent Assay
MVPA	Moderate-Vigorous Physical Activity
EDTA	Ethylenediaminetetraacetic acid
W	Watts
EXSS-IRB SOP	Exercise and Sport Science Institutional Review Board Standard Operating Procedures
DAIDS	Division of AIDS
AE/SAE	Adverse Event/Serious Adverse Event
UPIRSO	Unanticipated Problems Involving Risks to Subjects or Others
DSMB	Data and Safety Monitoring Board
APL	Applied Physiology Laboratory

1 Introduction

This document is a protocol for a human research study. This study will be conducted according to US and international standards of Good Clinical Practice (FDA Title 21 part 312 and International Conference on Harmonization guidelines), applicable government regulations and Institutional research policies and procedures.

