Specific Aim 1: To compare the metabolic responses immediately and 1 hr after HIIT compared to MICT matched for total energy expenditure, vs no exercise in 14 adults with T1D. Metabolism will be defined as energy expenditure (via indirect calorimetry), carbohydrate metabolism (tricarboxylic acid intermediates), and fat metabolism (acylcarnitines, respiratory exchange ratio).

Specific Aim 2: To evaluate key counter-regulatory/metabolic hormones (i.e. cortisol, lactate, glucagon, and insulin) during and after HIIT, MICT, and control (CON) sessions and the change in glycemia (using continuous glucose monitoring and glycemic cutpoints [<70 mg/dL, 70 - 180 mg/dL, >180 mg/dL]) for 48 hrs post exercise.

[figure not shown]
Specific Aim 3: To explore the modulatory effect of physiological variables on metabolism, including biological sex, lean body mass and visceral fat (measured from dual energy x-ray absorptiometry). Body fat percentage, lean mass, and visceral fat will be used to characterize the sample; the relationship of these variables with metabolomic intermediates will be assessed.

3 Study Design

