3.1 General Design

In a randomized controlled cross-over design, fourteen adults (7 females, 7 males) with T1D of at least 1-year duration and HbA1c $<9\%$ will undergo three conditions, in a randomized order: 1) high intensity interval training exercise session (HIIT) at 90% peak oxygen consumption (VO_2 peak); 2) moderate intensity exercise session (MICT; 65% VO_2 peak; or 3) a control session (CON; no exercise) (Figure 2).

Subjects will be asked to arrive to the laboratory after an overnight fast (8 hrs) and their usual dose of insulin administered the day prior, with no morning mealtime insulin the day of testing. The lower and higher limit for pre-exercise (i.e. fasted) glucose concentration (i.e. 10 minutes prior to the exercise start time) will be set at 90 and 250 mg/dL, respectively, and the session will be rescheduled if the pre-exercise glucose value is not in range or if hypoglycemia (blood glucose: <70 mg/dL) occurs within an hour of exercise start time. Subjects will also be asked to arrive to testing sessions following a 12 hour fast from caffeine and alcohol and to abstain from physical activity for 24 hours prior to testing. Subjects will complete one electronic contact (phone/email screening) and up to five in-person sessions (enrollment; baseline testing; three conditions [HIIT, MICT, CON]) over the course of 4 weeks

All data collection will be conducted by the Principal Investigator and Research Assistants. All subjects will report to the Applied Physiology Laboratory in [name] for consenting, enrollment, testing, and exercise sessions.

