5.2 Statistical Methods

For aim 1, changes in the first principal component, as well as any additional components for which the associated eigenvalue is greater than one, will be evaluated using paired t-tests at the 2-sided 0.05 level. Changes in individual metabolic intermediates will be evaluated using paired t-tests at the 2-sided 0.01 level. Differences in metabolomics and counterregulatory hormones markers between treatment regimens will be evaluated using two-way ANOVAs [regimen (HIIT vs. MICT vs. CON) \times time (base vs. immediate post vs. 1h post)]. Exploratory analysis of the modulatory effects of sex on metabolomics markers will be evaluated using separate regimen-by-sex mixed factorial ANOVAs [regimen \times sex], at each time point.

For aim 2, CGM data will be evaluated as previously recommended; data will be aggregated over the 24hrs; area under the curve data will be compared across trials.(25) Counter-regulatory hormones will be evaluated using a two-way mixed factorial ANOVA. Activity data will be captured to potentially be used as a covariate when collating CGM data.

For aim 3, spearman correlations will be completed to understand associations between metabolomics outcomes and physiological variables (i.e. body fat, lean mass, visceral fat).

6 Safety and Adverse Events

Risks associated with participating in this study are **possible**. In-test monitoring by the research team, who are certified fitness professionals trained in CPR/AED, are in place to ensure the safety of all subjects. Personnel trained in phlebotomy and with radiation exposure training will complete the blood draws and DXA scans, respectively.

In accordance with the Exercise and Sport Science Institutional Review Board Standard Operating Procedures (EXSS-IRB SOP), 3 trained research personnel (for safety purposes per IRB procedures) will perform cardiorespiratory fitness testing. Other precautions include: licensed medical professional (MD, ATC) on call, operational AED, and a land line within 10 feet of the testing in order to make emergency call, if required. Additionally, the lab is located within 500 feet of the University Athletic Training facility. If a cardiovascular event does occur, 911 will be called; UNC Hospitals and Emergency room are in very close proximity to the lab.

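### Aim 3 correlates metabolites with body composition across 7 men and 7 women without adjusting for sex, so where both variables differ by sex the coefficient can reflect sex, or mask a within-sex association

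*Combined protocol and SAP*

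**What the plan says.** The aim, in section 2 (Study Objectives), is "To explore the modulatory effect of physiological variables on metabolism, including biological sex, lean body mass and visceral fat". For the body-composition variables it adds that "the relationship of these variables with metabolomic intermediates will be assessed". Sex and body composition are thus listed as separate modulators. Section 1.1 (Background) likewise names obesity, biological sex and lean mass as distinct possible influences on the metabolic response.

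The method in section 5.2 is that "spearman correlations will be completed to understand associations between metabolomics outcomes and physiological variables", the variables being body fat, lean mass and visceral fat. The Study Summary gives the same method: "Spearman correlations between metabolomic outcome and physiological variables". Neither place mentions stratification, partialling or any covariate for these correlations, and neither gives a significance level for Aim 3. The sample in section 3.1 is "fourteen adults (7 females, 7 males) with T1D of at least 1-year duration".

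Sex is analysed elsewhere in section 5.2: "Exploratory analysis of the modulatory effects of sex on metabolomics markers will be evaluated using separate regimen-by-sex mixed factorial ANOVAs", run at each time point, with no body-composition term. The possible covariates named in sections 4.1 and 5.2 are diet, activity and, in women only, salivary estradiol. All are conditional. None is sex, and none is tied to the Aim 3 correlations. Section 3.2b ranks these outcomes as tertiary.

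**The concern.** An unqualified correlation in 14 people is most naturally read as one coefficient over everyone. Half the sample is of each sex by design, so sex is a fixed two-group split running through the data. If men and women differ on a body-composition measure and also on a metabolite, a pooled rank correlation is pulled away from zero even when the two are unrelated among men and unrelated among women. If the two differences have opposite signs, the pull is negative and can cancel or reverse a real within-sex association.

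What is at stake is whether Aim 3 can separate two of the modulators it names. A coefficient reported as a lean-mass or visceral-fat finding might be a sex difference under another label, and might guide later hypotheses as such.

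**Working it through.** **Plan's own figure.** There is none to reproduce. Section 5.1 gives N = 12 (14 enrolled) from effects of a single HIIT or MICT bout. No power, precision or alpha is stated for the Aim 3 correlations.

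**Inputs.** From the plan: 7 men and 7 women, Spearman correlation. Assumed: two-sided 5%; sex gap *d* in body composition and *m* in the metabolite, both in within-sex SDs; normal variables within sex.

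**Step 1: the pull, by formula.** With equal numbers of each sex and within-sex correlation ρ, the pooled population (Pearson) correlation is

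r = (ρ + d·m/4) / √[(1 + d²/4)(1 + m²/4)]

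- ρ = 0, d = 2, m = 1: 0.5 / √(2 × 1.25) = 0.32. This is an apparent association with none within sex.
- ρ = 0, and either gap zero: r = 0. There is no pull.
- ρ = 0.5, d = 2, m = −1: (0.5 − 0.5) / √(2 × 1.25) = 0. A real within-sex association disappears.

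**Step 2: rejection rates by simulation.** n = 7 + 7, ρ = 0, 40,000 data sets per setting. The adjusted test centres ranks within sex and uses n − 3 = 11 df.

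| Body-composition gap (SD) | Metabolite gap (SD) | Mean pooled Spearman | Pooled rejects | Sex-partialled rejects |
|---|---|---|---|---|
| 2 | 0 | 0.00 | 5% | 5% |
| 0.5 | 0.5 | 0.06 | 6% | 5% |
| 1 | 0.5 | 0.11 | 7% | 5% |
| 1 | 1 | 0.21 | 11% | 5% |
| 1.5 | 1 | 0.28 | 17% | 5% |
| 2 | 0.5 | 0.18 | 10% | 5% |
| 2 | 1 | 0.33 | 22% | 5% |
| 2 | 1.5 | 0.45 | 40% | 5% |

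With 12 completers (6 + 6), the 2 and 1 SD setting gives a mean of 0.33 and 19% rejection.

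**Step 3: cost in degrees of freedom.** The smallest correlation detectable with 80% power, by Fisher's z, is tanh[(1.96 + 0.84)/√k].

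- Pooled, k = 14 − 3 = 11: 0.69.
- Partialled for sex, k = 10: 0.71.
- One sex alone, k = 7 − 3 = 4: 0.89. Fully separate analyses are therefore not a useful substitute.

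**Step 4: cost when the metabolite's sex gap comes wholly through body composition.** Centring then removes genuine body-composition variation as well. Simulated power at two-sided 5%:

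| Body-composition gap (SD) | Within-sex correlation | Pooled | Sex-partialled |
|---|---|---|---|
| 1 | 0.5 | 49% | 38% |
| 2 | 0.5 | 69% | 37% |
| 2 | 0.6 | 86% | 52% |

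In the second row the metabolite's sex gap is 0.5 × 2 = 1 SD. That is the same pair of sex gaps (2 and 1 SD) that gave 22% false positives in Step 2. The pooled coefficient alone cannot tell the two situations apart.

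**The case against.** Four counter-arguments deserve weight.

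1. **Pooled and adjusted coefficients answer different questions**, the total and the within-sex association. Section 1.1 describes lean mass as a major site of glucose disposal, so a sex difference that acts through lean mass is plausible, and Step 4 shows what adjustment then loses. A reader might infer that the adjusted coefficient should simply replace the pooled one at no cost. The plan and the figures do not support that. This objection stands, and it is why both should be reported.

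2. **The bias is conditional.** A reader might infer that all the Aim 3 associations will be partly sex differences. They will be only where both variables differ by sex. When either gap is absent the pooled rate stays at about 5%, and with small gaps it is 6% to 7%. The documents give no sex gap for any measure, and section 3.4 caps BMI below 30. This stands as a limit on size.

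3. **Sex is not ignored.** The regimen-by-sex ANOVAs can flag which metabolites differ by sex, and so which correlations need caution. That mitigates the problem. But those models contain no body-composition term and leave the correlations unadjusted.

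4. **Aim 3 is exploratory and tertiary, in a pilot-funded study, with no stated test level.** This also stands. The rejection rates above apply only if the correlations are tested at 5%; the shift in the coefficient does not depend on that.

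A reader might also infer that the plan ties body composition to metabolite levels rather than to responses. Section 5.2 speaks only of outcomes and section 2 of intermediates. The form of the outcome is not specified, so that reading is not supported and this point does not rely on it.

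**Conclusion.** The point holds as a conditional one. As written, the Aim 3 correlations cannot separate body composition from sex for any metabolite and measure that both differ by sex. Over the assumed gaps (0.5 to 2 SD for body composition, 0.5 to 1.5 SD for the metabolite) and with no within-sex association, the pooled test rejects about 6% to 40% of the time at a nominal 5%. The sex-partialled test stays at about 5%. Opposite-signed gaps can mask a real association.

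This rests on reading the unqualified correlation as pooled over both sexes, on a 5% level that the plan does not state for Aim 3, and on sex gaps that are assumptions rather than figures from the documents. No primary or secondary conclusion is affected.

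**What to change.** In section 5.2, for Aim 3:

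- Prespecify a Spearman correlation partialled for sex (ranks centred within sex, n − 3 df), reported beside the pooled coefficient.
- Mark sex on the scatter plots.
- State that a body-composition association distinct from sex will be claimed only from the adjusted coefficient, and that the pooled one describes the total association.

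This is a cheap improvement: SAP wording, with no new data, visits or participants. It is not free. It uses one degree of freedom (detectable correlation 0.69 to 0.71) and lowers power where the metabolite's sex difference acts through body composition, for example from 69% to 37% at a 2 SD gap and a within-sex correlation of 0.5. Keeping the pooled coefficient in the report preserves that information.

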6.1 Definitions

Unanticipated Problems Involving Risk to Subjects or Others

Any incident, experience, or outcome that meets all of the following criteria:

- Unexpected in nature, severity, or frequency (i.e. not described in study-related documents such as the IRB-approved protocol or consent form, the investigators brochure, etc)
- Related or possibly related to participation in the research (i.e. possibly related means there is a reasonable possibility that the incident experience, or outcome may have been caused by the procedures involved in the research,
- Serious (as defined below) “Serious” is different than “severe” as reported in the CTC criteria that applies a grade to the AE.

Adverse Event

An **adverse event** (AE) is any symptom, sign, illness or experience that develops or worsens in severity during the course of the study. Intercurrent illnesses or injuries should be regarded as adverse events. Abnormal results of diagnostic procedures are considered to be adverse events if the abnormality:

- results in study withdrawal
- is associated with a serious adverse event
- is associated with clinical signs or symptoms
- leads to additional treatment or to further diagnostic tests
- is considered by the investigator to be of clinical significance

Serious Adverse Event

Adverse events are classified as serious or non-serious. A **serious adverse event** is any AE that is:

- fatal
- life-threatening
- requires or prolongs hospital stay
- results in persistent or significant disability or incapacity
- a congenital anomaly or birth defect
- an important medical event

Important medical events are those that may not be immediately life threatening but are clearly of major clinical significance. They may jeopardize the subject and may require intervention to prevent one of the other serious outcomes noted above. For example, drug overdose or abuse, a seizure that did not result in in-patient hospitalization, or intensive treatment of bronchospasm in an emergency department would typically be considered serious.

Serious adverse events that meet the following criteria will be reported to the IRB:

“Unanticipated problems involving risks to subjects or others” (UPIRSO) refers to any incident, experience, or outcome that:

- is unexpected (in terms of nature, severity, or frequency) given (a) the research procedures that are described in the protocol-related documents, such as the IRB-approved research protocol and informed consent document; and (b) the characteristics of the subject population being studied;
- is related or possibly related to a subject's participation in the research; and
- suggests that the research places subjects or others at a greater risk of harm (including physical, psychological, economic, or social harm) than was previously known or recognized.

All adverse events that do not meet any of the criteria for serious should be regarded as **non-serious adverse events**.

Adverse Event Reporting Period

The study period during which adverse events must be reported is normally defined as the period from the initiation of any study procedures to the end of the study procedures follow-up. For this study, the study procedure follow-up is defined as 30 days following the last administration of study procedures.

Post-study Adverse Event

All unresolved adverse events should be followed by the investigator until the events are resolved, the subject is lost to follow-up, or the adverse event is otherwise explained. At the last scheduled visit, the investigator should instruct each subject to report any subsequent event(s) that the subject, or the subject's personal physician, believes might reasonably be related to participation in this study.

6.2 Recording of Adverse Events

At each contact with the subject, the investigator must seek information on adverse events by specific questioning. Information on all adverse events will be recorded immediately in the subject file. All adverse events occurring during the study period must be recorded. The clinical course of each event should be followed until resolution, stabilization, or until it has been determined that the study participation is not the cause. Serious adverse events that are still ongoing at the end of the study period must be followed up to determine the final outcome. Any serious adverse event that occurs after the study period and is considered to be possibly related to the study treatment or study participation should be recorded and reported immediately.

6.3 Reporting of Serious Adverse Events and Unanticipated Problems

Any study-related unanticipated problem posing risk of harm to subjects or others, and any type of serious adverse event, must be reported to the clinical members of the team (informal DSMB) and the UNC IRB.

6.4 Stopping Rules

If two serious adverse events, related to the study procedures occur the study would be stopped. In addition, if two or more subjects experience the same or similar Grade 3 adverse event or serious adverse event, the study will be stopped. This study will not involve a formal data and safety monitoring board or committee. Adverse events will be reviewed by clinical members of the study team ([name], [name], [name], [name]). The PI will remain in contact with all study subjects and keep track of adverse events.

6.5 Data Handling and Record Keeping

Each subject and their associated information will be identified by a 4-digit alpha-numerical identification code. Subjects will be identified by this code only when labeling any data collection sheets or computer printouts. Code lists linking the subject identification number and their name and email address will be viewed by the research team only, and will be stored in a secure filing cabinet in the Applied Physiology Laboratory (APL) with the consent forms. This list will serve as the only link between a subject's name and ID code and will be destroyed (shredded by the principle investigator immediately after the study has been completed). Email addresses and phone numbers will be obtained solely for the purpose of contacting subjects to schedule testing and data collection times. All data will be stored in electronic format on both the data collection computer and the principle investigator's personal computer. Computer access will be protected via confidential passwords, and backup devices will be stored under lock-and-key in the APL.

6.6 Data Management

Data management will be completed using good clinical practices. Specifically, hard copy data sheets/case report forms will be used to capture initial data. This will then be transferred by a member of the university research team to Excel (Microsoft Office). Once in excel the PI and university research team will review the hard copy and electronic file to ensure correct transfer of the data. Data will be screened for mis-entries by evaluating the range, mean, standard deviation, and median for each outcome variable, in addition to visual inspection of frequency plots. In the case of extreme values, the original source of the data will be double-checked to ensure that the information has been accurately collected and recorded. If the inspection of the data source does not reinforce the accuracy of the data, the data point will be omitted. Electronic data obtained from the study will be stored forever and the data of paper material will be stored for five years since the study is completed. After that, paper material will be shredded by the PI. Participants will not be identified in any report or publication about this study. Although every effort will be made to keep research records private, there may be times when federal or state law etc. requires the disclosure of such records, including personal information. If disclosure is ever required, UNC-Chapel Hill will take steps allowable by law to protect the privacy of personal information. In some

cases, subject's information in this research study could be reviewed by representatives of the University, research sponsors, or government agencies (for example, the FDA) for purposes such as quality control or safety.

7 Study Finances

7.1 *Funding Source*

This study is funded by a pilot grant through the North Carolina Diabetes Research Center, awarded to [name]

7.2 *Subject Stipends or Payments*

Subjects will receive up to \$125 for their participation. Compensation will be prorated, with each visit compensated at \$31.25. Free parking will also be provided for all testing and training visits.

8 Publication Plan

Plans for publication are in place following successful completion of study data collection. These plans will be decided upon by the PI and collaborators who will discuss how best to present findings.

9 References

